9.1 Statistical Hypotheses and General Statistical Approach

The primary objective is to understand the outcome of using the Mosie kit for Intracervical insemination, i.e. pregnancy rate after its use. Specifically the hypothesis is as follows.

Primary hypothesis 1: Pregnancy rates using the at-home insemination Mosie Kit to deposit semen near or at the cervix (i.e. intracervical insemination) are equivalent or better than traditional in doctor's office intrauterine insemination (IUI). Conversely the null hypothesis is that the pregnancy rates using the at-home insemination Mosie Kit to deposit semen near or at the cervix do not have higher rates of pregnancy than in doctor's office IUI.

Analysis: Comparison of total rates of pregnancy using the Mosie Kit to the 10-20% rate reported for IUI by the American Pregnancy Association.

Primary Hypothesis 2: Pregnancy rates of LGBTQ couples or single women using the Mosie Kit where the female has no know fertility issues will be higher than that of heterosexual couples with a known fertility cause or those that are designated as having an unexplained fertility issue. The alternative hypothesis is that people with no known

fertility issues using the Mosie Kit will have less pregnancies than heterosexual couples with known fertility issues.

Analysis: Rate of pregnancy using the Mosie Kit will be obtained for the following groups: LGBTQ couples where carrying female has no known fertility issues, LGBTQ couples where carrying female has a known fertility issue, Heterosexual people with no known fertility issue, Heterosexual people with a known fertility issue, Single females with no known fertility issue and Single females with a known fertility issue. The rates of each group will be analyzed using descriptive statistics and the aggregate of the 3 groups with fertility issues will be compared with the aggregate of the 3 groups without fertility issues. An ANOVA will be used to compare the differences between groups.

Secondary Hypothesis 1: The participants perceived the Mosie Kit to be easy to use for its intended purpose. The alternative hypothesis is that the participants perceive the Mosie Kit to be difficult to use for its intended purpose.

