Analysis: Descriptive statistics will be used to analyze perceived safety. Qualitative analysis will be used on any comments made related to safety. Rates of vaginal infections will be analyzed using descriptive statistics.

Secondary Hypothesis 5: The majority of participants indicate they have little to no safety concerns related to using the Mosie Kit. Alternative hypothesis is the majority of participants will be very concerned or extremely concerned about the safety of using the Mosie Kit.

Analysis: Descriptive statistics of self-reported level of concern. Additionally, safety measures such as hand washing, disposing of the syringe after use, and reading the instructions will be examined using descriptive statistics.

Tertiary Hypothesis 1: There will be higher pregnancy rates when using the Mosie Kit when the source of infertility is male-based than when it is female-based. The alternative hypothesis is there will be lower pregnancy rates when using the Mosie Kit when the source of infertility is male-based than when it is female-based.

Analysis: In addition to the descriptive statistics a t-test will be run to examine this hypothesis.

Tertiary Hypothesis 2: There is a difference in pregnancy rates of people with known fertility issues depending on the source of their infertility. Specifically, the following sources of infertility will be examined if sufficient data is available.

- o PCOS
- Endometriosis
- Low AMH or low ovarian reserve
- Low sperm count
- Sperm motility issues
- Unexplained infertility
- Erectile dysfunction
- Performance issues or sexual anxiety, or inability to orgasm with partner.

Page 27

- Vaginismus or vulvodynia
- Tilted uterus
- Multiple uterus/cervix
- Loss of a fallopian tube

The alternative hypothesis is that there will be no difference in the fertility rates associated with different sources of infertility.

Analysis: Descriptive statistics, t-test, correlations and multiple ANOVAs will be used to examine this hypothesis.

Tertiary Hypothesis 3: There will be a difference between individuals who perform 2 insemination instances as described in the instructions and those that follow a different schedule or dosage number. The alternate hypothesis is that there will be no difference between the individuals that perform the minimum 2 insemination instances and those that follow difference dosage schedule.

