Analysis: Descriptive statistics of pregnancy rates for groups with 1, 2, 3 and 4 or more inseminations per cycle will be used. These rates will then be compared to determine if there is a difference.

Tertiary Hypothesis 4: COVID-19 has affected people's family expansion plans. The alternate hypothesis is that COVID-19 has had no effect on people's family expansion plans.

Analysis: Descriptive analysis and a t-test will be conducted to examine this hypothesis.

Tertiary Hypothesis 5: There will be a decrease in pregnancy rates in those using the Mosie Kit during the Months of March - June.

Analysis: Descriptive statistics, graphing, ANOVA and multiple regression analysis will be used to examine this hypothesis.

Additional Analysis will also be conducted to explore why people might choose to use the Mosie Kit, how they actually use it, additional things they do when using the Mosie Kit to complement the experience, and whether they think their health care provider should recommend Mose as an conception option. Most of this analysis will be achieved using descriptive statistics, correlations, and t-tests.

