9.4 Statistical Analyses

9.4.1 General Approach

Statistical analysis will commence with descriptive statistics for each survey question and plotting of the individual data into scatter plots to understand the data distribution. If any information suggests corrective procedures should be employed, the appropriate transformation or non-parametric test will be used.

Categorical values will be reported using descriptive statistics and frequency of occurrence. Key categorical values will also be converted into a percentage of total responses in order to allow an understanding of the prevalence of the response in the sample. For continuous variables, the means with standard deviations, median and range will be reported.

Qualitative data is only expected as a response to two questions, an open ended safety question and an additional comments question. The responses will be evaluated and categorized. Then the frequency of each category will be provided.

For inferential tests such as t-tests and ANOVAs, a p-value of 0.05 and a confidence interval of 95% will be used for statistical significance. The type of hypothesis will determine whether the specific tests will be one-tailed or two-tailed. Hypothesis seeking to understand whether there is or is not a difference will use a two-tailed test while those seeking a greater than or less than relationship will use a one-tailed test. Correlations among some of the variables will also be examined as appropriate.

Statistical analysis process for each hypothesis has already been described in section 9.1. No baseline analysis is used for cross-sectional studies. No interim analyses are planned for cross-sectional one survey studies.

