[figure not shown]
How did you or your partner time your ovulation? (Select all that apply.) *
Count days in cycle
Track vaginal or cervical fluids
Tracking changes in the cervix
Use ovulation predictor kit
Use an app to estimate ovulation
Basal Body Temperature
Wearable device
Did not time ovulation
Did using Mosie result in a pregnancy? *
O Yes
O No
Back Next Page 10 of 20

[figure not shown]
Never submit passwords through Google Forms.

 $This \ content \ is \ neither \ created \ nor \ endorsed \ by \ Google. \ \underline{Report \ Abuse} - \underline{Terms \ of \ Service} - \underline{Privacy \ Policy}$

Google Forms

Page 56

[figure not shown]

Safe process

Enjoyable

	Very Easy	Easy	Neutral	Difficult	Very Difficult
To collect the semen/sperm sample in the cup?	0	0	0	0	0
To draw up the semen/sperm in the syringe?	0	0	0	0	0
Insert the Mosie syringe into the vagina up to the handles?	0	0	0	0	0
To deposit the semen/sperm at or near the cervix using the syringe?	0	0	0	0	0
My overall impression on the ease of use	0	0	0	0	0
					Page 12 of 20
submit passwords to	through Google Fo				

MOSIE-001 © 2020 Mosie Baby Page 59

MOSIE-001 © 2020 Mosie Baby

Page 60

Pulled the syringe plunger back and forth to confirm it was functioning.

My partner washed their hands

Use a sperm friendly-lubricant.

Thawed out donor sperm from sperm bank

Prepared all items and have them handy ready to use.

Washed the penis

that	apply)?*
	Lie down in a comfortable position.
	Relax
	Receive oral sex
	Stimulate clitoris
	Use any vibratory or non-vibratory stimulation device intravaginally
	Have an orgasm
	Other:
	erall, how well were you able to use the Mosie syringe to inseminate yourself our partner? * Very Able
	our partner? *
or y O O O	our partner? * Very Able Able Not Very Able
or y 0 0 0 0	Very Able Able Not Very Able Not Able at All Volume at All Volume at All Volume at All Volume at All Able at All Volume at All Able at All Able at All
or y O O O	Very Able Able Not Very Able Not Able at All Volong did you remain laying down after using the Mosie syringe? * Less than 15 minutes

Willelf best descri	ibes your lying position? *	
On my stomach	n	
On my side		
On my back		
On my back wit	th my hips elevated by a pillow	
Other:		
O No		
O		
What type of sam	ple did you use? *	
What type of sam	ople did you use? * rom a sperm bank (frozen)	
What type of sam	rom a sperm bank (frozen)	

0 2000	thank 50%	
O 51%-	70%	
O 71% -	80%	
O 81%-	90%	
O 90%-	95%	
O 96%-	100%	

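### Section 9.1 names t-tests and ANOVA for a yes/no pregnancy outcome and no method for proportions, so error control in sparse infertility-cause groups depends on choices left open

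*Combined protocol and SAP*

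**What the plan says.** The survey in Appendix A records the outcome with one item, "Did using Mosie result in a pregnancy", answered yes or no. Section 9.1 assigns these methods to it:

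- Primary Hypothesis 2 (with against without fertility issues, across relationship types): "An ANOVA will be used to compare the differences between groups".
- Tertiary Hypothesis 1 (male-based against female-based infertility): "In addition to the descriptive statistics a t-test will be run to examine this hypothesis".
- Tertiary Hypothesis 2 (12 listed causes): "Descriptive statistics, t-test, correlations and multiple ANOVAs will be used to examine this hypothesis".
- Tertiary Hypothesis 5 (use in March to June): "Descriptive statistics, graphing, ANOVA and multiple regression analysis will be used to examine this hypothesis".

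Section 9.4.1 adds that "a p-value of 0.05 and a confidence interval of 95% will be used for statistical significance". On sidedness, "Hypothesis seeking to understand whether there is or is not a difference will use a two-tailed test", which makes Tertiary Hypothesis 2 two-tailed; the directional Tertiary Hypothesis 1 is one-tailed. The same section has a general fallback: "If any information suggests corrective procedures should be employed, the appropriate transformation or non-parametric test will be used".

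The causes are to be examined only where there are enough data, but no threshold is given. Odds ratios appear only among the exploratory analyses in 9.4.3, where any new hypothesis is again to be tested by t-test or ANOVA. Chi-square, Fisher's exact test, logistic regression and intervals for proportions are not named anywhere.

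**The concern.** A t-test estimates each group's variance from the data. For a yes/no outcome the variance is fixed by the proportion, and a small group with no pregnancies has an estimated variance of exactly zero. The unequal-variance (Welch) form then treats that group's rate as known without error and can call an ordinary run of failures significant. The pooled form and ANOVA borrow variance from the other groups and largely avoid this.

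The plan does not say which form will be used, how small a cause group may be, or whether a cause is compared with another cause or with everyone else. Tertiary Hypothesis 2 divides part of a target of 500 respondents among 12 causes, so sparse groups are possible. At stake are a finding that one cause does worse when only a handful of users reported it, and confidence intervals that have no width or run below zero.

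**Working it through.** **1. The plan's own figure.** Section 9.2 gives a 95% margin of 4.4 points at 500 surveys and 5 points at 384. With half-width = 1.96 × √(0.25/N):

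- N = 500: 1.96 × √0.0005 = 4.38 points.
- N = 384: 1.96 × √0.000651 = 5.00 points.

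Both reproduce. They describe a proportion in the whole sample. No power or error rate is given for any t-test or ANOVA.

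**2. Inputs for the error rate.** From the documents: a binary outcome, alpha of 0.05, two-tailed for Tertiary Hypothesis 2. Not in the documents, so assumed and varied: the t-test version, the group sizes (5 to 50 in the smaller group, 10 to 450 in the larger) and a common pregnancy rate of 10% to 50%. The only benchmark in 9.1 is 10-20% for IUI.

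**3. One table by hand.** Take 0/10 against 10/100.

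- Welch: the small group's variance is 0 and the large group's is 0.1 × 0.9 × 100/99 = 0.0909. SE = √(0 + 0.0909/100) = 0.0302, t = 0.10/0.0302 = 3.32 on 99 df, p = 0.001.
- Pooled: variance = (9 × 0 + 99 × 0.0909)/108 = 0.0833. SE = √(0.0833 × (1/10 + 1/100)) = 0.0957, t = 1.04 on 108 df, p = 0.30.

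If the true rate is 10%, a group of 10 has no pregnancies with probability 0.9^10 = 34.9%. This is what drives the Welch error rate.

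**4. Exact two-sided type I error.** All pairs of independent binomial counts with the same true rate were enumerated. Tables with zero variance in both groups count as non-rejections.

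| Sizes | True rate | Welch | Pooled t | Chi-square |
|---|---|---|---|---|
| 10 v 10 | 10% | 0.9% | 0.9% | 0.9% |
| 10 v 20 | 10% | 4.9% | 3.7% | 3.7% |
| 10 v 50 | 10% | 26.3% | 4.3% | 4.3% |
| 10 v 100 | 10% | 34.7% | 4.3% | 4.3% |
| 5 v 100 | 10% | 58.6% | 5.2% | 5.2% |
| 30 v 200 | 10% | 8.6% | 4.1% | 4.1% |
| 10 v 100 | 20% | 11.3% | 3.8% | 4.0% |
| 10 v 100 | 25% | 7.0% | 4.3% | 4.7% |
| 10 v 100 | 35% | 7.3% | 4.7% | 4.9% |
| 10 v 100 | 45% | 5.4% | 4.9% | 5.1% |

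Fisher's exact test gives 2.4% at 10 v 100 with a 10% rate. Over the whole grid the pooled t-test runs from 0.9% to 7.6%, almost identical to chi-square. ANOVA with 12 groups, by simulation, runs from 3.9% to 5.5%.

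**5. Larger groups, as in Tertiary Hypothesis 1.** For 100 v 150 and 150 v 350 at rates of 10% to 35%, two-sided Welch gives 5.1% to 5.6% and pooled t 4.8% to 5.0%. One-sided, as 9.4.1 would require, and computed in one direction, Welch gives 4.0% to 4.8% and pooled t 5.0% to 5.5%.

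**6. Intervals.**

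- 0/10: the t-based 95% interval is 0% to 0%. The Wilson upper limit is 1.96²/(10 + 1.96²) = 3.84/13.84 = 28%.
- 1/10: the sample variance is 0.09 × 10/9 = 0.10, so SE = √(0.10/10) = 0.10. The t interval is 10% ± 2.26 × 10 points, or -13% to 33%. Wilson gives 2% to 40%.

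**The case against.** The strongest reply is that the tests as written do not inflate error. The documents never mention an unequal-variance t-test. The pooled form fits the text equally well and tracks chi-square closely, and ANOVA stays near 5%, so no error problem is shown for Primary Hypothesis 2. Tertiary Hypothesis 1 stays near 5% in larger groups. All of this stands.

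A reader might still infer that the plan carries a 35% false-positive rate, or that 35% is the worst case. The documents support neither. The figure needs the Welch form, about 10 people against 100 or more, and a 10% rate. Smaller groups give more and balanced small groups give less. A 10% rate is also the bottom of the IUI benchmark, while section 2.2 cites much higher cumulative results for home or intravaginal insemination: 25% to 69% by age group, 13 of 29 (45%) and 20 of 45 (44%). At such rates a 10 v 100 Welch test gives about 5-7%.

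A reader might also infer that rare causes will be reported as significantly worse. The limit to causes with enough data could remove those groups. But it has no threshold, and the 9.4.1 fallback has no defined trigger and names no test, so neither settles the matter in advance. Nor do the documents say that the multiple regression in Tertiary Hypothesis 5 is linear; the model type is simply not stated.

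**Conclusion.** The point holds as a specification gap. Section 9.1 applies methods for continuous data to a yes/no outcome, names no test or interval for proportions, and leaves open the t-test version and the smallest usable group. That much comes from the documents without assumptions.

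The size is conditional. With pooled t-tests or ANOVA, or in large groups, the practical effect on error rates is small. With a Welch test in a sparse cause group, the two-sided false-positive rate at a nominal 5% could lie anywhere from about 1% to about 59%, depending on group sizes and a pregnancy rate that the documents do not give. The zero-width interval for a group with no pregnancies is a separate defect and does not depend on the t-test version. The numerical risk belongs to Tertiary Hypothesis 2, not to the primary comparison.

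**What to change.** Amend 9.1 for every analysis of pregnancy:

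- Replace the t-test and ANOVA with a chi-square test, or Fisher's exact test where expected counts are small, with the cut-off stated.
- Report risk differences with Newcombe (Wilson-based) 95% confidence intervals.
- Where groups are large enough, add logistic regression adjusted for age. Do not adjust for cycles used: people who conceive normally stop using the kit, so cycles used is partly a consequence of the outcome. If a group has no pregnancies, ordinary logistic regression has no finite odds ratio, so name an exact or penalised method.
- State the minimum group size that counts as enough data to examine a cause.
- Respondents may report more than one cause, in which case the cause groups overlap. Compare each cause as present against absent rather than cause against cause. Such comparisons can be very unequal in size, which is where the Welch test is least reliable.

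The cost is SAP wording; no new data or participants are needed. The downside is that Fisher's test is conservative in very small groups (2.4% at 10 v 100 with a 10% rate), so some real differences in rare causes will be harder to show.

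### Tertiary Hypotheses 2, 3 and 4 name equality as the alternative, but the planned difference tests cannot support it, so a non-significant result is the only route to it

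*Combined protocol and SAP*

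**What the plan says.** Section 9.1 sets out each tertiary hypothesis with an alternative.

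- **TH2 (source of infertility).** The hypothesis is "There is a difference in pregnancy rates of people with known fertility issues depending on the source of their infertility". The alternative is "The alternative hypothesis is that there will be no difference in the fertility rates associated with different sources of infertility". Twelve sources are listed, and "the following sources of infertility will be examined if sufficient data is available"; no minimum group size is given. The methods are: "Descriptive statistics, t-test, correlations and multiple ANOVAs will be used to examine this hypothesis".
- **TH3 (number of inseminations).** The hypothesis is that following the two-insemination instruction and following another schedule give different results. "The alternate hypothesis is that there will be no difference between the individuals that perform the minimum 2 insemination instances" and those on another schedule. The analysis begins: "Descriptive statistics of pregnancy rates for groups with 1, 2, 3 and 4 or more inseminations per cycle will be used". It continues: "These rates will then be compared to determine if there is a difference". No test is named.
- **TH4 (COVID-19 and family plans).** The hypothesis is an effect and the alternative is no effect. The method is descriptive analysis and a t-test.

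Section 9.4.1 sets significance at 0.05 with 95% confidence intervals and adds: "Hypothesis seeking to understand whether there is or is not a difference will use a two-tailed test". Section 9.2 justifies the sample (500 desired, at least 384) only by the precision of a single overall percentage.

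**The concern.** In a t-test or ANOVA, equality is the null hypothesis. A small p-value is evidence against it; a large one shows only that the data did not rule it out. When equality is labelled the alternative and no margin or interval criterion is given, the only event under the plan that corresponds to accepting it is a non-significant test.

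The results are meant to be used. The objectives table in section 3 says the source analysis will inform whether the kit works better for a particular cause of infertility. Section 4.2 says the data on timing and number of inseminations will feed into clearer instructions. Section 10.1.3 allows aggregate results in publications and marketing. An uninformative comparison between small groups could therefore reach users as a finding that the cause of infertility, or the number of inseminations, does not matter.

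**Working it through.** **1. The plan's own precision figure.** Half-width = 1.96 × √(0.25/n).

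- n = 500: 1.96 × √(0.25/500) = 4.38 points, stated as 4.4.
- n = 384: 1.96 × √(0.25/384) = 5.00 points, stated as 5.

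Both reproduce. Both describe one proportion in the whole sample. Section 9.2 gives no power or precision for any comparison between groups.

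**2. TH2: group size.** The documents give none. An even split is assumed: 500/12 ≈ 42 per source (384/12 = 32).

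**3. TH2: chance of missing a doubling between two sources.** Base rates of 10-20% come from the IUI range in 9.1, and 35% from the upper end of the range in 4.1. Using them as group rates is an assumption. With p̄ the mean of the two rates:

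power = Φ[(d − 1.96 × SE0)/SE1], SE0 = √(2p̄(1−p̄)/n), SE1 = √((p1(1−p1) + p2(1−p2))/n).

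At n = 42:

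| Rates | d | SE0 | SE1 | Power | Missed |
|---|---|---|---|---|---|
| 10% vs 20% | 0.10 | 0.0779 | 0.0772 | 25% | 75% |
| 15% vs 30% | 0.15 | 0.0911 | 0.0896 | 38% | 62% |
| 20% vs 40% | 0.20 | 0.1000 | 0.0976 | 52% | 48% |
| 35% vs 70% | 0.35 | | | 91% | 9% |

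Exact binomial enumeration of the pooled z-test gives 74%, 61%, 48% and 8% missed, so the approximation is adequate. At 32 per source the formula gives 80%, 70%, 59% and 18%.

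**4. TH2: one overall ANOVA** (simulated, 12 groups of 42). With one source doubled, the difference is missed 80%, 68% and 55% of the time at base rates of 10%, 15% and 20%. With half the sources doubled, the figures are 49%, 21% and 5%.

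**5. TH2: what a null result would show.** The half-width of the 95% interval for a difference between two groups of 42, both at rate p, is 1.96 × √(2p(1−p)/42).

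- p = 15%: 1.96 × √(0.255/42) = 15.3 points.
- p = 35%: 1.96 × √(0.455/42) = 20.4 points.

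A higher base rate makes a doubling easier to detect but widens the interval, so equality is no better supported.

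**6. TH3.** Section 9.1 contrasts two inseminations with any other schedule. At N = 500 and 10% vs 20%:

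| Share in the two-insemination group | Power | Missed |
|---|---|---|
| 50% | 88% | 12% |
| 80% | 67-75% | 25-33% |
| 90% | 38-56% | 44-62% |

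The ranges depend on which group has the higher rate. At 15% vs 30% with an even split, 2% is missed. For the four-group comparison with an assumed split of 100/300/60/40 and only the smallest group doubled, simulated ANOVA misses 63%, 49% and 32% at base rates of 10%, 15% and 20%.

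**7. What a similarity claim would need.** For two one-sided 5% tests with 90% power on each and equal true rates, n per group = 2p(1−p)(1.645 + 1.282)²/m².

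- m = 10 points: 155 (p = 10%) to 275 (p = 20%).
- m = 5 points: 617 to 1,097, more per group than the whole study.

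Both margins are illustrations; the documents give none.

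**The case against.** Section 9.1 uses the word alternative loosely, for the opposite of the study's claim. It does so for Primary Hypothesis 2, the secondary hypotheses and TH1 as well. Swapping the labels changes no calculation, because the software will take equality as the null anyway. This stands: the effect lies in what may be concluded, not in the computed p-values.

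The analyses are tertiary, sections 4.1 and 9.1 make subgroup work depend on sufficient data, and 9.4.1 mentions 95% intervals. This also stands in part. However, sufficient is undefined, and 9.4.1 offers the intervals as a significance criterion, with no guidance on reading a wide one.

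A reader might infer that the plan instructs the authors to report p > 0.05 as no difference. It does not; no section writes such a rule, and the risk comes from the labelling and the absence of any other rule.

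A reader might also infer that a doubling would often be missed under both TH2 and TH3. For TH3 this fails when the groups are reasonably balanced or the base rate is 15% or more, as step 6 shows.

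Finally, small groups are not a documented fact. Respondents without a fertility problem drop out of TH2, which shrinks its groups. If the diagnosis item in Appendix A accepts several answers, the groups overlap and could be larger. The home-insemination pregnancy figures cited in section 2.2 are also mostly above 20%, where a doubling is easier to detect.

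**Conclusion.** The reversal holds on the plan's wording alone, for TH2, TH3 and TH4, at any group size. The planned comparisons cannot support the stated alternative, and the plan offers no route to it except non-significance.

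The practical size is conditional. For TH2, with about 42 people per source and base rates of 10-20%, a doubling between two sources is missed about 48-75% of the time, falling to about 9% at a 35% base rate. The interval is about ±15 points at a 15% rate. For TH3, a doubling is often missed only with a low base rate or very uneven groups. These figures do not apply to TH4, whose outcome is not a pregnancy rate.

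This is a correction to the hypotheses and their interpretation in tertiary analyses. It does not show that the overall sample size is wrong for its stated purpose.

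**What to change.** In section 9.1:

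1. For TH2, TH3 and TH4, make no difference (for TH4, no effect) the null hypothesis and a difference or effect the alternative.
2. For TH2 and TH3, report pregnancy-rate differences with 95% confidence intervals: each source against the rest, and two inseminations against other schedules, rather than all pairs. Twelve sources would give 12 × 11/2 = 66 pairs. Comparing 42 with the remaining 458 at 15% gives 1.96 × √(0.1275 × (1/42 + 1/458)) = 11.3 points, against 15.3 for a pair.
3. State that p > 0.05 is reported as inconclusive, not as no difference.
4. Make no similarity claim unless the whole interval lies inside a margin fixed before the data are opened, and accept that groups of this size will rarely allow one.

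The cost is a wording change and some added intervals, with no new data. The downside is that many small-group comparisons will have to be called inconclusive.
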